6.5 Sensitivity Analysis

A sensitivity analysis to explore the robustness of the efficacy results with respect to the protocol deviations will be performed using Per-Protocol population for all efficacy endpoints.

6.6 Subgroup Analyses and Effect of Baseline Factors

Due to the small sample size, no subgroup analysis is planned for this study.

6.7 Multiplicity Strategy

This is the proof of concept study and hence no multiplicity adjustments are planned.

6.8 Handling of Missing Data

Clarifications, wherever possible, will be obtained from the respective investigator for any missing data or for any illegible entry, unused or unauthenticated data. Subjects are required to have at least one post-treatment assessment to be included in the MITT population. Last Observation Carried Forward (LOCF) will be used for the imputation of missing values. Baseline values will not be carried forward for the imputation of missing values. Subjects discontinued from study will be excluded from the PP population.

Document Title:	Statistical Analysis Plan		
Version Number:	2.0	Date:	11 Nov 2019
Protocol Number:	SARO.16.004	Sponsor Name:	Zydus Discovery DMCC

7. ANALYSIS OF PHARMACOKINETIC ENDPOINTS

Blood samples for pharmacokinetic analysis will be collected on Visits 3, 4, 5, 6 and 7.

Samples on Visit 3 and Visit 7 will be collected at Pre-dose (0.0), 0.5, 1.0, 2.0, 3.0, 4.0, 6.0, 8.0, 10.0 and 24.0 hours post-dose. Only pre-dose (0.0) samples will be collected on Visit 4, Visit 5 and Visit 6. The following PK endpoints will be derived from the plasma concentration-time data for each subject using Phoenix® WinNonlin® professional software (Version 6.4 or higher) provided there are sufficient data available to estimate each PK parameter:

For Single Dose (i.e. for Visit 3)

- Peak Plasma concentration (Cmax)
- Time to reach peak Plasma concentration (Tmax)
- Area under Plasma concentration vs. time curve till the last time point (AUCt)
- Area under Plasma concentration vs. time curve extrapolated to the infinity (AUCi) after first dose
- Area under plasma concentration vs. time curve in a 24 h dosing interval (AUCtau) after first dose
- Elimination rate constant (Kel)
- Elimination half-life (t1/2)
- Apparent Volume of distribution (Vd/F)
- Apparent Clearance (CL/F)

For Multiple Dose (i.e. for Visit 7)

- Peak Plasma concentration (Cmax,ss)
- Time to reach peak Plasma concentration (Tmax,ss)
- Area under Plasma concentration vs. time curve till the last time point (AUCt)
- Area under plasma concentration vs. time curve in a 24 h dosing interval (AUCtau) after last dose
- Elimination rate constant (Kel,ss)
- Elimination half-life (t1/2,ss)
- Apparent Volume of distribution (Vd/F,ss)
- Apparent Clearance (CL/F,ss)
- Minimal or Trough plasma concentration (Cmin)
- Fluctuation index.
- Accumulation index calculated as a ratio of AUCtau (last dose)/AUCtau (first dose)

Document Title:	Statistical Analysis Plan		
Version Number:	2.0	Date:	11 Nov 2019
Protocol Number:	SARO.16.004	Sponsor Name:	Zydus Discovery DMCC

No value of K_{el} and related PK parameters will be reported for cases that do not exhibit a terminal log-linear phase in the concentration versus time profile for single or multiple dose PK parameters. All concentration values Below Limit of Quantitation (BLQ) will be set to zero before pharmacokinetic analysis. If the pre-dose concentration appears to be >5% of the C_{max} in any subject on Visit 3 (for single dose only), then the descriptive statistics will be presented including and excluding that subject's data.

The AUC values will be calculated using the linear trapezoidal method. Actual sampling times of individual subjects will be used in the PK analysis.

Descriptive summaries for plasma concentration (n, mean, standard deviation, median, minimum, maximum, geometric mean and coefficient of variation) will be presented by sample collection time points and by treatment group.

Line plots (Linear and semi-log) of the mean concentration versus time curves for each treatment from each of the Visit 3 and Visit 7 post dose plasma collections will be plotted. Individual graphs for each treatment will also be presented.

Descriptive statistics (n, mean, standard deviation, median, minimum, maximum geometric mean and coefficient of variation) will be used to summarize the estimated pharmacokinetic parameters at Visit 3 and Visit 7 by treatment group.

8. SAFETY ANALYSIS STRATEGY

Safety analyses will be conducted using the safety analysis set on a treatment-emergent basis.

8.1 Safety Endpoints

The safety endpoints are:

- Adverse events.
- Vital Signs (Systolic BP, diastolic BP, pulse rate, oral temperature and respiratory rate)
- Clinical laboratory testing (hematology, clinical chemistry and urinalysis)
- Twelve-lead electrocardiogram (ECG)
- Physical Examination.

Document Title:	Statistical Analysis Plan		
Version Number:	2.0	Date:	11 Nov 2019
Protocol Number:	SARO.16.004	Sponsor Name:	Zydus Discovery DMCC

8.2 Safety Hypothesis

There are no formal safety hypotheses in this study. The focus of the safety analysis will be a comprehensive descriptive assessment of the safety endpoints listed in Section 6.1.

8.3 Statistical Methods for Safety Analysis

Except otherwise stated, the analysis set for all safety analysis is the safety analysis set as defined in Section 2.2. Unless otherwise specified, all safety parameters will be summarized by treatment group by visit.

8.3.1 Extent of Exposure

Study duration is defined as the date of last visit minus the date of the baseline visit plus one. Treatment duration is defined as “the date of last treatment minus the date of the first treatment plus one. If the date of late application is not available, the date of the last visit during the treatment will be used in calculation. If the date of first treatment is not available, the date of baseline visit will be used in calculation. Study duration and the treatment duration will be summarized descriptively.

8.3.2 Adverse Events

The applicable definition of an Adverse Event (AE) is in the study protocol. All AEs occurring from when a patient signs informed consent to when a patient exits the study will be accounted for in the reporting. Analysis and presentation of AEs occurring during the screening period will be separated from those occurring during the investigational period where a comparative evaluation of treatment-emergent AEs is intended. A treatment-emergent AE is an event not present prior to exposure to investigational product or any pre-existing event that worsens following exposure to investigational product. The period for treatment-emergent AE analysis starts from the first exposure to the investigational product until the patient exits the study.

Descriptive summaries (frequencies and percentages) for specific AEs will be presented by system organ class and preferred term according to the Medical Dictionary for Regulatory Activities (MedDRA Version 19.1) dictionary by treatment group and overall. In addition to an overall presentation of all AEs, reports will be generated for special classes of AEs such as investigational product related AEs, serious AEs, Maximum severity and AEs resulting in treatment discontinuation by treatment group. These reports will be supported by individual patient listings, as necessary.

Document Title:	Statistical Analysis Plan		
Version Number:	2.0	Date:	11 Nov 2019
Protocol Number:	SARO.16.004	Sponsor Name:	Zydus Discovery DMCC

Adverse events will be counted by the number of events as well as the number of subjects. For the summaries which count the number of patients by treatment group and overall, multiple AEs with the same MedDRA preferred term within the same patient will only be counted once.

Descriptive summaries (frequencies and percentages) for number of subjects experiencing AEs will also be presented.

Only patient listings will be provided for AEs that occur after signing informed consent but prior to exposure to investigational product. These listings will comprise all events occurring during this period in any patient who consented to participate in the study.

These listings will at least contain but not limited to information such as onset and resolution times, maximum severity, causal relationship to study treatment and action taken.

8.3.3 Vital Signs

Descriptive summaries (N, mean, median, standard deviation, minimum and maximum values) of observed values and change from baseline in each vital sign parameter at each assessment visit will be presented. A listing will be provided for the vital signs parameter assessments.

8.3.4 Physical Examination

Physical examination results (normal/abnormal/not done) from scheduled visits will be summarized for each body system.

8.3.5 Laboratory Results

Laboratory values will be presented using the International System of Units (SI units). Clinical laboratory evaluations consist of hematology, clinical biochemistry and urinalysis. Observed and changes from baseline values will be summarized descriptively (N, mean, median, standard deviation, minimum, and maximum values) at each assessment. A summary table of the categorical grade shift changes using the normal ranges from baseline to last study visit will be provided.

For summary purposes, laboratory values that are listed as above or below particular thresholds will be numerically listed as above or below that threshold, respectively, by the minimum measured amount for that parameter. For example, if a parameter is measured to two decimal places, and has a result of “> 6” then, for summary purposes, the value of 6.01

Document Title:	Statistical Analysis Plan		
Version Number:	2.0	Date:	11 Nov 2019
Protocol Number:	SARO.16.004	Sponsor Name:	Zydus Discovery DMCC

will be used. Values with “<” or “>” will be classified as Low or High, respectively, unless such classifications aren’t applicable for that parameter, in which case they will be classified as Normal.

A listing will be provided which contains data for each laboratory parameter. In addition, a listing of all clinically significant abnormal values will be provided.

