- Visit 3:** The Randomization & Treatment Phase will include 6 outpatient visits over a period of 16 weeks, including the randomization visit. Patients will be randomly assigned to receive either Saroglitzaz magnesium (2 mg or 4 mg) or placebo orally once daily in addition to their ongoing treatment with UDCA (Patients unable to tolerate UDCA will receive only the investigational medicinal products), starting on Day 1 and continuing for 16 weeks. Efficacy and safety parameters will be assessed during each study visit as per the Schedule Visit Table.
- Visit 3.1:** Patient will visit study site at 2 weeks after randomization visit for LFTs. The LFTs will be performed at local laboratory.
- Visits 4, 5 and 6:** Patients will visit the study site at Week 4 (Visit 4), Week 8 (Visit 5) and Week 12 (Visit 6) for clinical assessment, dispensation and reconciliation of study drug, and measurements of efficacy endpoints.
- End-of-treatment Visit (Visit 7):** An End-of-double-blind treatment will occur at Week 16 and considered as End of Treatment visit. The clinical assessment, reconciliation of study drug, and measurements of efficacy and safety endpoints will be performed as per the study schedule.
- Safety Follow-up Visit (Visit 8):** A final post-treatment visit will occur 4 weeks (± 3 days) after the End-of-treatment Visit for safety monitoring. A clinical examination and safety lab assessment will be performed during this visit.

Patient withdrawal

In the event a patient is withdrawn from the study prematurely for any reason, the End of Treatment Visit procedures should be followed.

The Investigator may withdraw a subject from the study for any of the following reasons:

1. Subject who reports AE and if considered in Investigator's/Medical Expert's opinion

that it is not in the subject's best interest to continue.

2. Any subject found to have entered the study in violation of this protocol.
3. Subject's lack of compliance to the study protocol.
4. Any subject who wishes to withdraw his / her consent for participation in the study.
5. In case a subject becomes pregnant, then she will be withdrawn from the trial.
6. Any subject who requires the use of unacceptable concomitant medications as mentioned in exclusion criteria and restrictions.
7. Termination of study by sponsor, IRB/IEC, or the regulatory authority.

Discontinuation of Subject Investigational Product (IP)

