After screening, the eligible patients will be randomly assigned to one of the following treatment groups in addition to their ongoing treatment with UDCA (Patients unable to tolerate UDCA will receive only the investigational medicinal products) i.e., Saroglitzaz magnesium 2 mg, Saroglitzaz magnesium 4 mg, or placebo. Vital signs measurements, weight measurements, physical examination, and laboratory examination will be performed as mentioned in Table 1. Concomitant medications will be recorded. AEs will be noted, if any. Urine pregnancy test will be performed for women of childbearing potential. Subjects will undergo cardiac evaluation (ECG). A 4-week supply of study medication (one bottle) will be dispensed. Baseline quality of life assessment will be performed.

- **Visit 3.1 (Week 2±3 Days)**

Patient will visit study site at 2 weeks after randomization visit for LFTs. The LFTs will be performed at local laboratory.

- **Visit 4 (Week 4±3 Days), Visit 5 (Week 8±3 Days) and Visit 6 (Week 12±3 Days)**

Subjects will be undergo a physical examination and laboratory parameters (safety and efficacy) will be assessed as per Table 1. Vitals signs, body weight will be recorded.

AEs, if any, will be noted. Urine pregnancy test will be performed for women of childbearing potential. Concomitant medications will be recorded. Medication compliance will be checked. Medication will be dispensed on each visit for next 4 weeks.

- **End-of-treatment Visit 7 (Week 16±3 Days)**

Subjects undergo physical examination and laboratory parameters (safety and efficacy) will be assessed as per Table 1. Vitals signs and weight will be recorded. AEs will be noted, if any. Subjects will undergo cardiac (ECG) evaluation. Pregnancy test will be performed for all women of childbearing potential. Concomitant medications will be recorded. Medication compliance will be checked.

- **Safety follow-up Visit 8 End of Study (Week 20±3 Days)**

A safety follow-up visit will be performed 4 weeks after End-of-treatment Visit. Patients clinical examination and safety lab assessment will be performed as per Table 1.

Unscheduled visits- will be allowed any time during the study for assessment and management of AEs and any concurrent clinical conditions. Unscheduled visits shall be captured in the CRF.

- If further investigations are required in case of any AE, Investigator will assess the AE and take necessary action, if required.

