8.3.6 ECG

A 12-lead electrocardiogram (ECG) was performed at Screening, Baseline, Week 16 and safety follow-up visit at Week 20. ECG results (normal, abnormal clinically insignificant, abnormal clinically significant) will be summarized. Listing of the patient who had gone through the ECG examination will be presented.

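### The SAP's only laboratory shift table compares baseline with the last study visit, so shifts that arise on treatment and resolve before then are not counted by arm

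*SAP*

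**What the plan says.** SAP 8.3.5 specifies a single laboratory shift table: "A summary table of the categorical grade shift changes using the normal ranges from baseline to last study visit will be provided". No shift to the worst value, to Week 16 or by visit is named, and the SAP does not say which visit is the last one.

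The same section plans other laboratory outputs: observed and change values summarised at each assessment, with minimum and maximum; a listing of every laboratory parameter; and a separate listing of abnormal results judged clinically significant. SAP 8.3 makes summaries by treatment group and visit the default for safety parameters. Protocol 8.3.3 commits to frequencies of abnormal laboratory values by treatment group and visit, a table that SAP 8.3.5 does not mention.

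On timing, Protocol 7.2 has "End-of-treatment Visit 7 (Week 16±3 Days") as the last visit on treatment, followed at Week 20 by "Safety follow-up Visit 8 End of Study", where safety laboratory tests are taken. The protocol summary says "A final post-treatment visit will occur 4 weeks", give or take 3 days, after the end-of-treatment visit.

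**The concern.** A laboratory shift table shows how many patients in each arm moved from normal to abnormal after starting treatment. If its second time point falls about four weeks after dosing stops, it describes how patients look once off treatment. A reversible effect on an enzyme or blood count could be present in an active arm for weeks and leave no trace in the table, and the contrast with placebo would shrink because every arm is off study treatment by then.

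Safety and tolerability are stated objectives of this trial. The abnormalities most exposed are modest ones that neither stop treatment nor get recorded as adverse events, because no other output named in the SAP counts them by arm.

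**Working it through.** The plan states no figure for this point, so the check compares the text and works out dates.

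**1. Which visit is the last study visit?**
- Protocol 7.2 labels the Week 20 visit "Safety follow-up Visit 8 End of Study".
- SAP 2.5 equates completing the study with the Week 20 assessment.
- SAP 8.3.1 says "Study duration is defined as the date of last visit minus the date of the baseline visit plus one", but where it needs an on-treatment date it writes "the date of the last visit during the treatment will be used in calculation". The authors therefore had separate wording for an on-treatment visit and did not use it in 8.3.5.
- SAP 8.3.6 treats Week 20 as a visit like the others: the ECG "was performed at Screening, Baseline, Week 16 and safety follow-up visit at Week 20".

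Week 20 is the best reading for completers, but it is an inference.

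**2. How long after the end-of-treatment visit is the value taken?**
- Protocol summary and 7.1: 28 ± 3 days, which is 25 to 31 days.
- Protocol 7.2, with each visit having its own window: Week 16 is day 112 ± 3, or 109 to 115; Week 20 is day 140 ± 3, or 137 to 143. The shortest gap is 137 − 115 = 22 days and the longest is 143 − 109 = 34 days.

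**3. How many on-treatment visits feed the table for a completer?** Scheduled laboratory visits on treatment are Weeks 4, 8, 12 and 16; Week 2 adds liver tests at a local laboratory.

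| Reading of last study visit | Scheduled visits used | Counting local Week 2 liver tests |
|---|---|---|
| Week 20 | 0 of 4 | 0 of 5 |
| Week 16 | 1 of 4 | 1 of 5 |

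The Week 16 reading removes the off-treatment problem but still leaves out a shift that resolves by Week 16.

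**4. What do the other outputs give?**
- The maximum at a visit shows that at least one patient was high. It does not show how many, or whether they were normal at baseline.
- Listings hold every value but give no count by arm.
- Protocol 8.3.3's by-visit frequencies would count abnormal values at each visit. As described, they do not link a value to the patient's baseline category or give one count per patient across visits.
- Adverse event tables capture results that are clinically significant or change dosing (Protocol 6.2.2 and 9.4.1).

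No named output in either document counts patients per arm who moved from normal to abnormal at any time on treatment.

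**5. A possible example.** Creatine kinase had to be normal at Visit 1 (Protocol 4.3, criterion 9). The listed discontinuation criterion is above 5 times the upper limit of normal (Protocol 4.4.1), and statins are permitted with monitoring for toxicity (Protocol 5.8). An on-treatment value between 1 and 5 times the limit is new relative to Visit 1 and does not meet that criterion. If it is normal again at Week 20, the shift table does not count it. The example holds only if Table 1, which is not readable in the public copy, schedules creatine kinase at these visits.

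**The case against.** The strongest reply is that no information is lost. SAP 8.3.5 itself promises minima and maxima at each assessment, a full listing and a listing of clinically significant abnormalities, and with 12 patients per arm the listings can be read from end to end. Protocol 8.3.3's by-visit table has not been withdrawn: the SAP says it is based on protocol version 6.0, and its general by-visit default is compatible with that table. Results that matter clinically go to adverse event reporting. Safety is descriptive in this proof-of-concept study, and neither document promises a worst-value shift table.

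Most of this stands, and it limits the point to a missing count. It does not remove the point: a reader of the report will take the shift table as the summary of laboratory change, and its stated end point is poorly suited to that use.

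Three stronger readings are tempting, and the documents do not support them.
- A reader might infer a conflict with SAP 8, which says "Safety analyses will be conducted using the safety analysis set on a treatment-emergent basis". The only treatment-emergent period the SAP defines, for adverse events in 8.3.2, runs until the patient leaves the study. Week 20 lies inside it. The table is incomplete on that basis, but it does not contradict it.
- A reader might infer that the table mixes off-treatment values from completers with near-treatment values from withdrawals, and try to size this from the planned 20% dropout. Protocol 4.5 does ask for end-of-treatment procedures at withdrawal, but Protocol 4.4.1 follows patients stopped on listed laboratory criteria until values return to baseline. When their last value falls is unknown, so the split cannot be calculated.
- A reader might infer that the SAP has dropped the protocol's by-visit table. It has only failed to name it.

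**Conclusion.** The point holds in limited form. As written, the only laboratory shift table leaves out any shift that arises on treatment and resolves by the last study visit. For completers that visit is best read as Week 20, 22 to 34 days after the end-of-treatment visit, and no scheduled on-treatment laboratory result then enters the table. The core of the point survives a Week 16 reading.

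The loss is a per-arm count of on-treatment shifts, mainly for abnormalities below adverse event thresholds; the underlying data remain visible elsewhere. The number of shifts missed cannot be stated, because the documents give neither a rate of on-treatment shifts nor a rate of resolution. The conclusion assumes that safety laboratory tests are drawn at the on-treatment visits and at Week 20, as the protocol text indicates; which analytes are drawn at each visit cannot be confirmed without Table 1.

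This is a cheap improvement for the sponsor to consider. It does not threaten the trial's conclusions.

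**What to change.** In SAP 8.3.5:

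- Replace the present end point with a shift from baseline to the worst on-treatment value, from first dose to Week 16 or early end of treatment. Tabulate shifts to high and to low separately.
- State whether local Week 2 results and unscheduled results count towards the worst value.
- Show Week 20 in its own table, labelled as off treatment.
- Name the table of abnormal-value frequencies by visit and arm that Protocol 8.3.3 promises.

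The cost is a few more tables from data already collected. Worst-value shifts will be more frequent in every arm, including placebo, so the active arms must be read against placebo. Counting unscheduled results makes abnormalities easier to find in patients who are tested more often, which is why that rule should be stated in advance.
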